6.2 Informed Consent

The investigator or qualified designee must obtain written consent from each potential patient or each patient's Legally Acceptable Representative (LAR) prior to participating in a clinical trial. Consent must be documented on an IRB/EC approved consent form. A copy of the signed and dated consent form should be given to the patient before participation in the trial.

The initial informed consent form, any subsequent revised written informed consent form and any written information provided to the patient must receive the IRB/EC's approval/favorable opinion in advance before use. The patient or his/her legally acceptable representative should be informed in a timely manner if new information becomes available that may be relevant to the patient's willingness to continue participation in the trial. The communication of this information will be provided and documented via a revised consent form or addendum to the original consent form that captures the patient's dated signature or by the patient's legally acceptable representative's dated signature. Specifics about a trial and the trial population will be added to the consent form template.

CONFIDENTIAL Page 32 of 66

The informed consent will adhere to IRB/EC requirements, applicable laws and regulations and Sponsor requirements.

6.3 Screening

During screening period, written informed consent must be obtained prior to the initiation of trial treatment and before any protocol-specific procedures are performed. An additional consent for tumour biopsy will be requested. Screening vitals, laboratory tests, as described in the Schedule of Events, will be performed as per institutional practice and will be reviewed by the site PI/designee. The laboratory tests should be done ≤ 7 calendar days prior to the initiation of trial treatment. Re-screening can be done at the discretion of PI.

Radiological assessment and other investigations to document presence of disease should be performed within 28 days prior to C1D1. Documentation of serology status (HIV, HBV and HCV) will be done based on historical information. To be considered negative for active infection, following algorithm will be used:

- HBV: HBc antibody should be negative or if HBc antibody is positive, HBVDNA should be undetectable
- HCV: HCV antibody should be negative or if HCV antibody is positive, HCVRNA should be undetectable
- HIV: HIV antibody should be negative. (HIV 1/2 antibody should be negative unless positive result is considered false positive by PI).

Note: Patients who show evidence of hepatitis B infection (HBsAg positive [regardless of antibody status] or HBsAg negative but anti-HBc positive), need to be evaluated for initiation of HBV antiviral prophylaxis and should be closely monitored for HBV reactivation.

Covid-19 testing prior to enrollment may be done as per the institutional practice/local requirements.

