- 7. Patient with symptomatic uncontrolled brain metastasis. (Note: A scan to confirm the absence of brain metastases is not required. Patients whose brain metastatic disease has remained stable for ≥ 4 weeks (prior to the start of study treatment) following treatment of brain metastases are eligible. The patient can receive a stable dose of corticosteroids before and during the study if steroids were started at least 4 weeks prior to C1D1).
- 8. HIV positive patients who are on antiretroviral therapy OR active hepatitis C OR active hepatitis B virus infections.
- 9. Ongoing immunosuppressive therapy including systemic corticosteroids except as allowed per concomitant medication.
- 10. Known history of severe liver injury (e.g., alcoholic liver disease, primary biliary cirrhosis, ongoing extrahepatic obstruction caused by stones, cirrhosis of the liver or portal hypertension) as judged by investigator. (Note: Exception will be the patients with liver metastasis who can be enrolled in the study).
- 11. History of severe cutaneous reactions (e.g., Drug Rash with Eosinophilia and Systemic Symptoms (DRESS), Stevens–Johnson syndrome (SJS) or toxic epidermal necrolysis (TEN) in the past.
- 12. Active gastrointestinal tract disease with malabsorption syndrome or uncontrolled inflammatory gastrointestinal disease such as Crohn's disease or ulcerative colitis.
- 13. Myocardial infarction within 6 months before starting therapy, symptomatic congestive heart failure (New York Heart Association > Class II), unstable angina, or unstable cardiac arrhythmia requiring medication or clinically relevant findings in the ECG such as second-or third-degree AV block, significant prolongation of the QTcF interval, unless agreed between the investigator and the medical monitor.
- 14. Concurrent disease or condition that would interfere with study participation or safety, such as the following:
 - o Active, clinically significant infection requiring parenteral antimicrobial agent.
 - o Clinically significant bleeding diathesis or coagulopathy, including known platelet function disorder.
 - o Mood disorders like OCD, severe depression, history of suicidal attempt, schizophrenia etc. as per the investigator's discretion.
- 15. Concurrent medications or substances with the potential to affect the activity or pharmacokinetics of tenalisib, as reviewed and confirmed by medical monitor.
- 16. Pregnancy or lactation.

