4.2 Exclusion Criteria

Individuals who meet any of the following criteria will be considered ineligible to participate in the study:

- 1. Patients with HER-2 positive breast cancer
- 2. Patient receiving anticancer therapy (e.g., chemotherapy, biologic therapy, hormonal therapy or any other investigational product) within 4 weeks or 5 half-lives of the drug prior to C1D1, whichever is shorter. Treatment interval will be 6 weeks for nitrosoureas or mitomycin C.
- 3. Patient who has not recovered from acute toxicities (defined as NCI-CTCAE grade > 1) of previous therapy except treatment-related alopecia. (Note: Patient with any unresolved toxicities which in the opinion of PI are stable and controlled with medication can be enrolled in the study).
- 4. Patients who have had disease progression within 8 weeks of platinum chemotherapy. (Note: Patients who have had a disease-free interval of more than 8 weeks following platinum chemotherapy; and patients with previous neoadjuvant OR adjuvant platinum-based therapy can participate in the study).
- 5. Prior exposure to investigational or marketed PI3K inhibitors (e.g., idelalisib, copanlisib, duvelisib, umbralisib, alpelisib, buparlisib) given for treatment of breast cancer
- 6. Major surgery within 4 weeks of starting study treatment OR any patient who has not recovered from the effects of major surgery.
- 7. Patient with symptomatic uncontrolled brain metastasis. (Note: A scan to confirm the absence of brain metastases is not required. Patients whose brain metastatic disease has remained stable for ≥ 4 weeks (prior to the start of study treatment) following treatment of brain metastases are eligible. The patient can receive a stable dose of corticosteroids before and during the study if steroids were started at least 4 weeks prior to C1D1).
- 8. HIV-positive patients who are on antiretroviral therapy OR active hepatitis C OR active hepatitis B virus infections.
- 9. Ongoing immunosuppressive therapy including systemic corticosteroids except as allowed per concomitant medication.
- 10. Known history of severe liver injury (e.g., alcoholic liver disease, primary biliary cirrhosis, ongoing extrahepatic obstruction caused by stones, cirrhosis of the liver or

CONFIDENTIAL Page 28 of 66

- portal hypertension) as judged by investigator. (Note: Exception will be the patients with liver metastasis who can be enrolled in the study).

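### The section 6.3 rule for no active hepatitis B leaves out HBsAg, so an HBsAg-positive, anti-HBc-negative patient is classed as negative with no HBV DNA result required

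*Protocol*

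**What the plan says.** Exclusion criterion 8, in the synopsis and in Protocol section 4.2, lists "HIV-positive patients who are on antiretroviral therapy OR active hepatitis C OR active hepatitis B virus infections". It does not say what makes a hepatitis B infection active.

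Protocol section 6.3 supplies the working definition, introduced by "To be considered negative for active infection, following algorithm will be used". The hepatitis B line is "HBc antibody should be negative or if HBc antibody is positive, HBVDNA should be undetectable".

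A Note below the list concerns "Patients who show evidence of hepatitis B infection (HBsAg positive [regardless of antibody status] or HBsAg negative but anti-HBc positive". These patients "need to be evaluated for initiation of HBV antiviral prophylaxis and should be closely monitored for HBV reactivation". The Note does not ask for HBV DNA and does not exclude anyone.

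On the source of the data, 6.3 says "Documentation of serology status (HIV, HBV and HCV) will be done based on historical information". Table 3 lists hepatitis B serology with historical data acceptable, and Table 5 has HIV, HBV and HCV status as a screening item. The SAP does not change any of this.

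**The concern.** The rule and the Note disagree about the same patient. If she is HBsAg-positive and anti-HBc-negative, the rule calls her negative for active infection at its first branch. The Note says she shows evidence of infection. The authors clearly had this pattern in mind, because the Note applies to HBsAg positivity whatever the antibody status.

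The ordering is also hard to defend. An HBsAg-negative, anti-HBc-positive patient must show undetectable HBV DNA. An HBsAg-positive, anti-HBc-negative patient need not show any DNA result.

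At stake is whether such a patient can start a PI3K delta/gamma inhibitor with her viral load unknown, in a protocol that itself asks for close monitoring for HBV reactivation in patients with evidence of hepatitis B infection. This is a question of eligibility and patient safety, not of analysis.

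**Working it through.** The plan states no figure here to reproduce. The check is to apply the rule as written to every combination of its inputs, and then to apply the proposed wording.

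Inputs:
- Rule as written (6.3, hepatitis B line): negative if anti-HBc is negative, or if anti-HBc is positive and HBV DNA is undetectable.
- Note (6.3): applies if HBsAg is positive, or if HBsAg is negative and anti-HBc is positive.
- Proposed rule: negative if HBsAg and anti-HBc are both negative, or if either is positive and HBV DNA is undetectable.

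There are 2 × 2 = 4 serological patterns and, with DNA undetectable or detectable, 4 × 2 = 8 rows.

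| HBsAg | anti-HBc | HBV DNA | Rule as written | DNA needed? | Note applies? | Proposed rule |
|---|---|---|---|---|---|---|
| − | − | undetectable | negative | no | no | negative |
| − | − | detectable | negative | no | no | negative |
| − | + | undetectable | negative | yes | yes | negative |
| − | + | detectable | not negative | yes | yes | not negative |
| + | − | undetectable | negative | **no** | yes | negative, DNA now needed |
| + | − | detectable | **negative** | **no** | yes | **not negative** |
| + | + | undetectable | negative | yes | yes | negative |
| + | + | detectable | not negative | yes | yes | not negative |

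Reading the table:
1. The Note applies to three of the four patterns. For two of them the rule as written also requires HBV DNA. For the third, HBsAg-positive and anti-HBc-negative, it does not.
2. That third pattern is classed as negative whether or not virus is detectable, because DNA is never consulted.
3. The proposed wording changes the classification in one row of the eight (HBsAg positive, anti-HBc negative, DNA detectable) and adds a DNA requirement in that row and its undetectable partner. The other six rows are unchanged. In particular, an anti-HBc-positive patient with undetectable DNA can still enter, as the plan intends.

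The other provisions that might close the gap:
- Protocol 5.2 asks for prophylactic antivirals in chronic HBV carriers. That is treatment, not a viral-load check.
- Inclusion criterion 7e caps ALT and AST at 3 × ULN, or 5 × ULN with liver metastasis or involvement, and Chemistry Panel I is scheduled on treatment (Table 5). Neither measures virus.
- Exclusion criterion 18 lets an investigator exclude a patient for an active infection that would impair her ability to receive therapy or whose control therapy might jeopardise. It does not mention HBV DNA, and the protocol's own hepatitis B rule would still label her negative.

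**The case against.** The best reply is that HBsAg is missing from one line, not from the screening section. A site cannot apply the Note without knowing HBsAg, so 6.3 read as a whole does not overlook this patient: she is evaluated for prophylaxis and monitored. Criteria 8 and 18, the carrier rule in 5.2, the transaminase cap and the scheduled chemistry give further protection, and a careful investigator would probably ask for HBV DNA anyway.

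Most of this stands. It reduces the risk, and it rules out any claim that HBsAg-positive patients go unprotected. It does not close the gap, because none of these provisions requires HBV DNA or reverses the label the rule assigns.

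Two stronger readings are tempting, and the documents do not support them.

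- **A harm pathway through liver toxicity.** A reader might link the gap to the transaminase rises reported with tenalisib in section 1.4 and to the steroid steps in Table 7. Those rates come from patients with haematological malignancies and say nothing about HBV status, so they do not measure this defect. Section 7.6 makes Table 7 guidance, subject to the investigator's judgement and intended for events the investigator considers related to tenalisib. A rise attributed to hepatitis B falls outside it.
- **A contradiction on HIV.** Criterion 8 bars HIV-positive patients only if they are on antiretroviral therapy, while 6.3 says "HIV 1/2 antibody should be negative unless positive result is considered false positive by PI". A reader might infer that an untreated HIV-positive patient can enter. She cannot at a site that applies both texts: they can be met together, and the stricter 6.3 rule already screens her out. This is a wording mismatch, not a defect of substance.

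**Conclusion.** The concern holds for hepatitis B. As written, the 6.3 rule classes an HBsAg-positive, anti-HBc-negative patient as negative for active infection without an HBV DNA result, and the Note below it contradicts that label. This is an incorrect classification by a stated rule rather than a missing detail, because criterion 8 relies on the word active and gives no other definition.

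The size is small. One of four serological patterns is affected. Its frequency is not given in the documents and none is assumed, so the number of affected patients among the 40 could be zero. No sample size, error rate, endpoint or analysis population figure changes.

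The conclusion rests on reading the 6.3 list as the operative test for criterion 8, which is what its introductory sentence says. Admission of anti-HBc-positive patients with undetectable DNA is a deliberate allowance and is not challenged.

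**What to change.** Reword the hepatitis B line in Protocol section 6.3 to: *HBsAg and HBc antibody should both be negative, or, if either is positive, HBV DNA should be undetectable.* Keep the Note as it stands, so that patients admitted with evidence of infection but undetectable DNA are still evaluated for prophylaxis and monitored.

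The cost is a one-line edit. Hepatitis B serology is already a screening item and may come from historical records. The extra work is at most an HBsAg result where none is on file, and an HBV DNA test in a patient who is HBsAg-positive and anti-HBc-negative.

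SAP section 5.1 reports that the study closed early, so the correction matters mainly for any later protocol that reuses this screening text. Section 1.5.2 of the protocol says that the selected dose is meant to go forward.

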6.3.1 Assignment of screening and randomization numbers

All consented subjects who undergo at least one post-consent procedure will be given a unique screening number that will be used to identify the subject for all procedures that occur during screening. Post confirmation of the eligibility, subject will be assigned a randomization number.

CONFIDENTIAL Page 33 of 66

Protocol No. RP6530-2101 Version 1.0, Dated June 29, 2021

Figure 2: Schema for screening

| Screening period | | | | Dosing |
|------------------|---|--|---|------------------------------|
| | | Day -28 to Day | 0 | Day 1 |
| | | | | |
| Patient consent | • | Disease assessment Radiological assessment Laboratory assessment Other assessments as part of eligibility assessment | Eligibility confirmation Collection of blood sample for cytokine/chemokines Tumour biopsy in consented patients | First Dose of the study drug |

Note: Post eligibility confirmation, the biopsy will be performed in approximately 10-12 patients who have consented for biopsy, prior to the first dose on C1D1. Eligible patients who do not consent for biopsy will also be enrolled into the study. Blood will be collected in all patients for cytokine/chemokine analysis.

6.3.2 Medical history

Basic demographic and baseline characteristics will be collected during screening. In addition to the evaluation of a patient's medical history in terms of study eligibility, all relevant medical conditions will be documented on the appropriate eCRF. Events occurring after signing of informed consent but prior to initiation of tenalisib, unless serious and due to a protocol mandated procedure, should be recorded on the Medical History eCRF.

The patient's entire oncology history will be collected on the appropriate eCRF including date of diagnosis for cancer (and other malignancy, if applicable), prior surgeries / treatments received for cancer, dates of treatment administration, best response achieved, date of progression and its assessment, and *BRCA* mutation status (if known).

6.3.3 Prior and Concomitant Medication Review

Prior medication: The investigator/qualified designee will review prior medication use, including any protocol-specified washout requirement, and record prior medication taken by the patient within 28 days before starting the trial (i.e., C1D1). Treatment for the disease for which the patient has enrolled in the study will be recorded separately and not listed as a prior medication.

Concomitant medication: The investigator or qualified designee will record medication, if any, taken by the patient during the trial.

6.3.4 Physical Examination

Full physical examination: The investigator/qualified designee will perform a complete physical exam during the screening period and as defined in Schedule of Events. Physical examination will include systemic examination (General Appearance, HEENT, neck,

CONFIDENTIAL Page 34 of 66

cardiovascular, lungs, abdomen, lymph nodes, genitourinary (as applicable), extremities, neurological, skin, and musculoskeletal). Physical examination also includes measurement of accessible nodes and the size of the spleen and liver. Clinically significant abnormal findings should be recorded as medical history.

Abbreviated (symptom directed) physical examination: For cycles that do not require a full physical exam per the Schedule of Events, the investigator or qualified designee will perform a directed physical exam as clinically indicated depending on assessment of tumour, prior to trial treatment administration. After the first dose of trial treatment new clinically significant abnormal findings should be recorded as AEs.

6.3.5 Vital Signs

Vital signs include temperature, pulse, respiratory rate, weight and blood pressure and should be recorded as per institutional practice. Historical data can be used for height. Vitals will be done prior to the administration of study treatments, at the time points specified in schedule of events.

6.4 Laboratory Investigations

Laboratory tests for hematology, chemistry and urinalysis are specified in **Table 3**.

Table 3: Laboratory Tests for Hematology, Chemistry and Urinalysis

| Hematology | Chemistry Panel I | Chemistry Panel II | Urinalysis | Other |
|-------------------------------|--------------------------|--------------------|-------------------|-----------------------|
| Hematocrit | Total bilirubin | Total Cholesterol | Blood | Serum β-hCG |
| Hemoglobin | Alkaline phosphatase | Triglyceride (TG) | Glucose | Urine pregnancy test |
| Platelet count | ALT | LDL | Protein | PT and INR |
| WBC (Total and differentials) | AST | HDL | Specific gravity | Serology (Hepatitis |
| | LDH | T3, T4, TSH | Microscopic | B, Hepatitis C, HIV)- |
| Absolute | | | exam ^b | Historical data is |
| neutrophil count | GGT |  | | acceptable. |
| - | Blood glucose | | | |
| | Albumin | | | |
| | Total protein | | | |
| | Urea or BUN ^a | _ | | |
| | Creatinine | | | |
| | Sodium | | | |
| | Potassium | | | |
| | Calcium | | | |
| | Phosphorous | | | |
| | Chloride | | | |

^a Blood Urea Nitrogen is preferred, if not available Urea may be tested.

NOTE: Laboratory results obtained during Screening should be used to determine eligibility criteria. In situations where laboratory results are out of reference range, the

CONFIDENTIAL Page 35 of 66

^b Microscopic exam, if abnormal results are noted

investigator may opt to retest the patient and the subsequent within range screening result may be used to confirm eligibility.

Blood drawn for these tests will be specified in informed consent form (ICF) as per the site ICF requirements. *All safety laboratory investigations will be performed locally at the site*. Screening labs will be done within 7 calendar days prior to the initiation of trial treatment. If these initial examinations are obtained within 72 hours of Cycle 1 Day 1, the labs need not be repeated on C1D1 again.

6.5 12-Lead Electrocardiograms

A single 12-lead electrocardiogram (ECG) will be obtained at designated time points using local ECG machine that automatically calculates the heart rate and measures PR, QRS, QT, and corrected QT (QTc) intervals. ECG will be performed after the patient has at least a 5-minute rest. Additional ECGs will be obtained if clinically indicated.

Table 4 : ECG time points

| Days | Time points | |
|-------------|--------------------------------------|--|
| Screening | Within last 28 days | |
| C1D1 | Pre-dose | |
| At other | Pre-dose C2D1, C3D1 and at EOT visit | |
| time points | | |

